1.4. Special Conditions for Use Statement

- Vivatmo *pro*TM should only be used as directed in the Vivatmo *pro*TM Instructions for Use (IFU).
- Vivatmo *pro*TM should not be used in critical care, emergency care, or in anesthesiology.
- Vivatmo *pro*TM results should not be used as a sole parameter for the diagnosis or screening of airway diseases.
- Vivatmo *pro*TM measurement procedure requires patient cooperation and patients must be capable of a complete breathing maneuver (exhalation) and cooperating with all necessary requirements for test performance.
- Vivatmo *pro*TM should not be used with infants or by children under 7 years of age.
- Patients should refrain from eating and drinking for 1 hour before exhaled NO measurement.
- Recent intake of nitrate rich foods, such as lettuce, spinach, beets, walnuts, peanuts, and animal organs, can lead to increased FeNO levels.
- Alcohol ingestion reduces FeNO levels in patients with asthma and healthy subjects.
- Patients should not smoke for 1 hour before measurement, and any short-term and long-term active and passive smoking history should be recorded. Smoking reduces FeNO levels.
- Vivatmo *pro*TM results obtained from patients who smoke should only be considered after accounting for the subject's smoking history and the potential impact on FeNO levels.
- When possible, perform serial FeNO measurements at the same time of the day.
- Regardless of displayed results clinicians must follow standard clinical care practices for symptoms of chest tightness, shortness of breath, and coughing or wheezing for decisions relative to treatment,
- For prescription use only.

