4.2. Subject Inclusion Criteria

Patients meeting the following criteria may be included:

1. Subject is 7 to 80 years of age.*
2. Subject is newly diagnosed or has a confirmed past diagnosis of uncontrolled asthma determined by a physician and as defined below:
 - (a) Symptoms of cough, recurrent wheezing, recurrent difficulty breathing, or recurrent chest tightness are present.
 - (b) Symptoms occur or worsen at night or with exercise, exposure to allergens and irritants, changes in weather, hard laughing or crying, stress, or other factors.
3. Has been identified as a candidate for inhaled corticosteroid (ICS) treatment and is willing and able to comply with the recommended ICS treatment plan.
4. Is willing and able to perform Vivatmo *pro*TM testing at initial and follow-up study visits.
5. Subject or legal guardian is willing and able to provide informed consent.

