4.3. Subject Exclusion Criteria

Patients meeting the following criteria should be excluded:

1. Subject has used inhaled corticosteroids or oral corticosteroids within 4 weeks prior to enrollment; or subject has taken biologic immunotherapy medications.**
2. Subject has other current serious medical conditions (other than asthma) that may impair study participation and measurements unless deemed acceptable by the study site investigator including, but not limited to:
 - (a) respiratory diseases,
 - (b) cardiovascular diseases,
 - (c) neuromuscular diseases, or
 - (d) chest wall or spinal column deformities.
3. Subject is suffering from acute upper or lower respiratory infection including:
 - (a) common cold,

- (b) influenza, or
- (c) pneumonia.

4. Subject is pregnant.
5. Subject is currently participating in another interventional pharmaceutical study or undergoing another asthma therapy.
6. Subject has engaged in any of the following within one hour prior to fractional exhaled nitric oxide (FeNO) measurement:
 - (a) food and beverage (other than water) intake,
 - (b) caffeine (coffee, tea, etc.) intake,
 - (c) nicotine (including cigarettes, cigars, pipe, nicotine chewing gum, nicotine patch, snuff, vapor e-cigarettes, etc.) intake,
 - (d) strenuous exercise, or
 - (e) use of a short-acting inhaled bronchodilator, leukotriene modifier, or any rescue inhaler.
7. Subject has a history of prior or excessive alcohol use*** or drug abuse within last 12 months.
8. Subject has a familial or close relationship with study personnel (device instructors or administrators).
9. Subject is unwilling or unable to perform Vivatmo pro™ and spirometry testing (pulmonary function test) at initial and follow-up study visits and to comply with treatment plan.
10. Subject or legal guardian is unwilling or unable to provide informed consent.

Inclusion/Exclusion Notes:

(*) *Including 30% pediatric cases (age 7 to 17) and 70% adult cases (age 18 to 80)*

(**) *Subjects undergoing a corticosteroid “wash-out” are not allowed.
Subjects on leukotriene modifiers (such as Singulair) prior to or during the study are allowed.
Antihistamine usage prior to and during the study is allowed.*

(***) *Excessive alcohol use defined as more than 2 alcoholic drinks per day (14 per week) for adult males and more than 1 alcoholic drink per day (7 per week) for adult females.*

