6.4. Patient Screening and Consent

Subjects will optimally be selected from those already scheduled for clinic visits. Prior to study participation and the collection of any study data the PI, and designated study coordinator, will obtain informed consent from each subject who meets inclusion/exclusion criteria. The date of informed consent and confirmation of compliance with study inclusion/exclusion criteria will be recorded on the designated study CRF. Upon completion of consent subjects will be enrolled into the study and this will optimally occur after confirmation of a clinical diagnosis of asthma and prior to prescription of inhaled corticosteroid (ICS) treatment. Diagnosis of asthma may require spirometry measurement.

6.5. Guidance for Preparing and Training Study Subjects on Use of the Vivatmo *pro*TM

Study Coordinators, designated testers, and study subjects should wash their hands prior to using the Vivatmo *pro*TM device for testing. The study coordinator should explain the test to the subject and demonstrate appropriate techniques. It is recommended that study coordinators train subjects (especially children) on proper grasping technique and exhalation technique prior to performing the first Vivatmo *pro*TM measurement. Training may involve practice with holding and positioning the handheld component and practicing a controlled exhalation using a “Flow Be” floating ball toy (where constant exhalation flow/rate causes a toy ball to be suspended in air), using a musical instrument, or other equivalent simulation. The test assumes a full inhalation before beginning.

The subject may need to be prompted or encouraged to “blow” the air from their lungs. Enthusiastic coaching of the subject using appropriate body language and phrases, such as “keep going”, may be required. Encouragement, detailed but simple instructions, lack of intimidation, and visual feedback from the instrument are important in helping children to perform the test.

It is helpful to observe the subject to check for distress and to observe the Vivatmo *pro*TM base station display during the test to help ensure correct effort. If the patient feels “dizzy” testing should be stopped. Well-fitting false teeth should not be routinely removed, since they preserve oropharyngeal geometry and results may generally be better with them in place. Correct patient performance (exhalation flow rate) is required for the measurement to be considered valid.

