7. DATA COLLECTION, HANDLING AND RECORD KEEPING

7.1. Study Management Documentation and Logs

Participating clinical sites will maintain a Patient Screening Log and a Subject Enrollment Log. The Patient Screening Log should contain a nonconfidential (coded) listing of potential study patients screened at the clinic for study participation and identify those that were included in the study, those that were not included in the study, and the reasons why patients were not included (excluded). The Subject Enrollment log should identify enrolled study subjects and their assigned Study Subject ID.

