8.4. Analysis of Secondary Endpoints

The relationship between changes of FeNO-values and clinical assessments (spirometry, ACQ-questionnaire) will be assessed by Spearman's rank correlation.

Repeatability will be estimated together with the 95%-confidence interval as pooled standard deviation (mean of measurement pair < 50 ppb) and CV (mean of measurement pair ≥ 50 ppb), respectively, using the residual variance component resulting from a random effects ANOVA (as used in CLSI EP05 guideline) with patient and visit as random factors. Technically, the CV is estimated as $100 \times$ standard deviation applying the random effects ANOVA on ln-transformed values. The resulting pooled repeatability is hereby estimated taking in account conditions of variability over sites and operators.

The *success rates* (proportion of patients with successful measurement within FAS) will be reported. The number of attempts necessary to obtain 2 valid replicate measurements will be tabulated in contingency tables by visit.

9. COMPLIANCE WITH GOOD CLINICAL PRACTICES (GCP), ETHICAL CONSIDERATIONS, AND ADMINISTRATIVE ISSUES

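### Could subjects who fail to give a valid FeNO reading drop out of the success-rate denominator, and is success defined closely enough to report?

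*Combined protocol and SAP*

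**What the plan says.** Success rate is the third secondary objective (2.2) and a secondary outcome measure (3.2). Section 8.4 gives its analysis: "proportion of patients with successful measurement within FAS) will be reported". The next sentence of 8.4 adds a table, by visit, of how many attempts were needed to reach two valid readings. Section 8.1 places in the FAS every patient for whom a FeNO measurement was intended. The Per Protocol Set additionally requires a valid reading at each of the two visits.

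On eligibility, section 4.3 opens with "Patients meeting the following criteria should be excluded", and its item 9 reads "Subject is unwilling or unable to perform Vivatmo pro™ and spirometry testing (pulmonary function test) at initial and follow-up study visits", with compliance with the treatment plan added. Inclusion 4 in section 4.2 is the mirror image: willing and able to do the device "testing at initial and follow-up study visits". Section 1.4 sets the same condition for ordinary use: "patients must be capable of a complete breathing maneuver (exhalation").

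On sequence, section 6.4 has consent obtained from patients who meet the criteria and compliance with the criteria recorded on a CRF. It then says "Upon completion of consent subjects will be enrolled into the study". Sections 3.5 and 6.2 put device training and measurement after that. The Screening Log (7.1) lists the patients left out "and the reasons why patients were not included (excluded").

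On attempts, the synopsis, 3.5 and 6.6 allow 10 exhalations per visit to reach two valid readings. Section 6.7 repeats that total, writes it as 2 x 5, and adds that each valid reading has to come within 5 attempts.

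**The concern.** A patient's inability to use the device is seen for certain only when the patient exhales into it, and that happens after enrolment. A subject with ten invalid attempts is in the FAS, yet also looks like someone described by exclusion 9. Exclusion 6 ("Subject has engaged in any of the following within one hour prior to fractional exhaled nitric oxide (FeNO) measurement") is tied to the study measurement too, so the list does not seem confined to facts fixed at consent. If a site or the sponsor reclassified such subjects as ineligible, the failures would leave the denominator. The error could only go upward, and in an open-label study the decision would follow the observed failure.

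In addition, a successful patient is not defined. One valid reading is enough for the primary comparison, two are requested at each visit, and the Per Protocol Set asks for one at both visits. A rate over both visits would also count a subject who missed Visit #2 as a failure of device use. Finally, a reading obtained on attempt 6 to 10 with none before it meets the total of 10 but not the limit of 5 in section 6.7.

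At stake is the only objective that asks whether subjects can operate the device.

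**Working it through.** The plan gives no expected success rate, target or sample size for this endpoint, so there is no figure to reproduce. Its sample sizes of 10 and 13 (synopsis) concern the primary comparison and do not bear on this point. The only input taken from the documents is the planned enrolment of 120. All failure, attendance and validity rates below are assumed.

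**1. Which reading of the denominator do the passages support?**

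- 8.4 names the FAS as the denominator, and 8.1 defines it by intention to measure. A subject who was handed the device and failed is inside it.
- 6.4 settles eligibility at consent. Exclusion 9 is therefore a judgement made beforehand, in line with 1.4.
- Exclusion 9 covers the follow-up visit and treatment compliance. Neither can be known at enrolment, so the wording looks forward. Applied afterwards, it would also remove Visit #2 failures and non-compliers, which nothing in 8.1 suggests.
- The matters in exclusion 6 (food, caffeine, nicotine, exercise, inhaler use) are known before the subject exhales. They set no precedent for excluding on a test result.
- 6.7 answers an invalid reading with a repeat. It does not call for removal.
- The Per Protocol Set asks separately for valid readings, which implies that FAS subjects may lack them. This is supporting evidence only, because that condition also screens out missed visits.

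**2. What would the other reading cost?** With k failures at Visit #1, the rate is (120 − k)/120 if they are kept and (120 − k)/(120 − k) = 100% if they are removed. Limits are exact (Clopper-Pearson). For n successes out of n the lower limit is 0.025^(1/n).

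| k (assumed) | Kept (95% CI) | Removed (lower limit) |
|---|---|---|
| 3 | 97.5% (92.9–99.5) | 100% (96.9) |
| 6 | 95.0% (89.4–98.1) | 100% (96.8) |
| 12 | 90.0% (83.2–94.7) | 100% (96.6) |

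The 100% follows from the removal itself and says nothing about the device. The two intervals come from nested sets of the same subjects, so whether they overlap has no inferential meaning.

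**3. Missed Visit #2.** If 6 or 12 of 120 do not return and all attendees succeed, a Visit #2 rate over the FAS is 114/120 = 95.0% or 108/120 = 90.0%, against 100% of attendees.

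**4. Attempt limit.** Assume independent attempts, each valid with probability p, and q = 1 − p, at one visit. Two valid readings within 10 attempts has probability 1 − q^10 − 10pq^9. Each reading within 5 attempts has probability (1 − q^5)^2.

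| p (assumed) | Two in 10 | Each within 5 | Gap (points) |
|---|---|---|---|
| 0.3 | 85.1% | 69.2% | 15.9 |
| 0.5 | 98.9% | 93.8% | 5.1 |
| 0.6 | 99.8% | 98.0% | 1.9 |
| 0.7 | 100.0% | 99.5% | 0.5 |
| 0.8 | 100.0% | 99.9% | 0.1 |

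**5. One or two readings, one or both visits.** Under the same model, with independent visits, at least one valid reading in 10 at one visit has probability 1 − q^10. This is 99.9% at p = 0.5. The strictest reading, two readings each within 5 attempts at both visits, gives (1 − q^5)^4 = 88.1%. At p = 0.3 the two figures are 97.2% and 47.9%. At p of 0.7 or more, every version is 99% or higher.

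**The case for a change.** The strongest case for a change is that the definition really is absent. Two analysts could follow 8.4 to the letter and print different percentages for the same data, and at low validity the spread is wide (47.9% to 97.2% at p = 0.3). The attempts table describes use but does not define the rate. No sentence forbids treating a failed subject as ineligible after the fact, the bias would run one way, and a few sentences in 4.3, 6.7 and 8.4 would close all three gaps without new data.

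Most of the factual part stands: success is undefined by number of readings, visit and handling of absence, and 6.7 carries a per-reading limit that the synopsis, 3.5 and 6.6 do not repeat. The denominator part does not stand, because removing an enrolled subject would depart from 8.1 and 8.4 and is not something those sections leave open. The wide spread requires a device that rejects most exhalations. In that event the by-visit table of attempts would show the difficulty, whatever headline rate was chosen. On the attempt limit, 6.7 itself ties the two figures together as 2 x 5. A total cap and a per-reading cap can coexist, so the passages differ in completeness more than in substance.

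**Conclusion.** The concern does not call for a change. As written, the plan keeps enrolled subjects without a valid reading in the success-rate denominator, so the jump to 100% (from 95.0% with 6 assumed failures, or from 90.0% with 12) arises only under a reading that 6.4, 8.1 and 8.4 do not support. Patients turned away beforehand as unable to do the test are a fair restriction to the population described in 1.4, and the reasons are kept in the Screening Log.

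What is left is missing detail on a descriptive secondary rate that has no target, no test and no decision attached. An analyst would naturally report it per visit, for one and for two valid readings, over the FAS with missed visits shown. The data needed are already collected by visit, and the attempts table is already planned. The attempt-limit wording moves the rate by 0.5 points or less if at least 70% of attempts are valid, and by about 5 points at 50%. These sizes rest on assumed failure, attendance and validity rates and on independent attempts. The conclusion about the denominator rests on the text alone.

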9.1. Adherence to Protocol, Good Clinical Practices (GCP), and Applicable Regulations

The study shall be conducted as described in this protocol, according to good clinical practices (GCP), in compliance with the principles set forth in the Declaration of Helsinki, and according to applicable U.S. Federal Regulations.

The PI shall ensure that all work and services described herein shall be conducted in accordance with the highest standards of medical and clinical research practice. The PI will provide copies of the protocol to all co-Investigators or other staff responsible for study conduct.

9.2. Institutional Review Board

The protocol, as well as the Informed Consent template, will be approved by a central IRB (WIRB - Western IRB, Puyallup, WA) prior to the start of the study.

The Institutional Review Board (IRB) will review and approve enrollment of subjects into this study. The PI shall obtain written confirmation from the IRB that the protocol and other applicable documents have been approved. The study cannot begin until approval is received.

If the study continues beyond the time period specified by the IRB, the PI would request a renewal of the study. The renewal application will include any applicable documents required for the duration of the study. The PI will obtain written confirmation from the IRB that the study has been renewed. The PI will inform the IRB when the study has been terminated and obtain written confirmation from the IRB/IEC of the study closure.

9.3. Subject Protections

It is the responsibility of the PI to assure that informed consent is obtained from each subject or legal guardian in accordance with current regulations. The content of the informed consent will conform to current ICH and FDA guidelines for the protection of human subjects, and/or to the specific IRB requirements. The informed consent form must be in English, signed and dated by the subject, or legal guardian, and Investigator, or designee.

Each subject will be given verbal and written information describing the nature and duration of the study. This will take place under conditions where the subject, and/or legal guardian, has adequate time to consider the potential risks associated with his/her participation in the study. All subjects' questions must be answered adequately to ensure that they have the information they require to make an informed decision about participation in the study. The signed informed consent form will be filed in a study Investigational Site File (ISF) along with all other Case Report Forms (CRFs).

No subject names, medical record numbers, or other personally identifying information will be used as part of the study or transmitted to the sponsor or designee. Case Report Forms (CRFs) will not contain any confidential information linking the date or outcome result to a subject. Only the study site will have the information that links a subject to his/her identifying information. Subjects will only be referred to by using their unique Subject ID number.

9.4. Confidentiality

This study protocol, study, documentation, and all other information generated, will be held in strict confidence by the PI and their representatives. No information concerning the study or the data will be released to any unauthorized third party without prior written approval by the Sponsor.

9.5. Monitoring

The Study Manager and Clinical Monitor, as representatives of the Sponsor, have the obligation to follow this study closely. The Study Manager and/or Clinical Monitor will visit the study facility/site as needed, in addition to maintaining necessary contact by telephone, tele/video-conference, e-mail, facsimile, and/or letter communication. Monitoring of this study will entail review of the required study documents, such as Case Report Forms (CRFs), investigational testing results, quality control test results, staff training records, and other activities as deemed necessary during monitoring visits.

9.6. Study Deviations

All effort must be made to avoid deviations from the protocol, regulations, or GCPs. If a deviation occurs, it must be reported to the study Sponsor, or designee, and recorded by site personnel in a deviation report describing the deviation and corrective/preventative actions; which is kept with the ISF and a copy provided to the sponsor, or designee, for the TMF. The study manager will determine whether the site's IRB/IEC must be informed

9.7. Serious Adverse Event (SAE) Reporting

A significant adverse event (SAE) is one that has a serious adverse effect on the health or safety of a study subject, or causes any medical problem, life-threatening problem, or death of the study subject.

All SAEs should be recorded by the PI and reported by the PI to the Sponsor, or designee, and to the IRB within 24 hours after the PI becomes aware of the SAE. The Sponsor will collect adverse event information and may report serious and unanticipated adverse events to the FDA.

9.8. Risks

There are no known direct risks to patient health.

9.9. Potential Benefits

There is no guaranteed benefit to a subject for participation in this study. Subjects are to be treated for their asthma per their physician's standard of care.

9.10. Compensation

Subjects may be offered a gift card, (worth no more than \$25 per visit) for study participation. Sites may be compensated for time and effort completing study tasks.

All study instruments and supplies will be provided to the participating sites at no charge. Subject medications will not be covered by the Study Sponsor.

9.11. Quality Assurance Audit

In the event that PI is contacted by a Regulatory Agency in relation to this study, the PI will notify the Sponsor immediately. The PI or designee must be available to respond to reasonable requests and audit queries made during an audit process. The PI must provide the Sponsor with copies of all correspondence that may affect the review of the current study (e.g., Form FDA 483, Inspectional Observations, and warning letters).

9.12. Publication Policy

The data and results from this study are the sole property of the Sponsor. The Sponsor will have the right to access and use all data and results generated during the clinical study. The PI will not use the study related data without the written consent of the Sponsor for any purpose other than for study completion or for generation of publication material. The Sponsor must approve all material for publication prior to submission.

